## 12. Adverse Events

An adverse event (AE) is any untoward medical event that occurs to a study participant once the individual has signed the informed consent form until the study participant's last study visit.

Examples include:

- Any sign, symptom, or physical examination finding that worsens in nature, severity or frequency compared to baseline

A serious adverse event (SAE) is one that meets any of the following criteria:

- Results in death
- Is life threatening
- Requires inpatient hospitalization or prolongation of an existing hospitalization
- Results in persistent or significant disability/incapacity
- An important medical event that may not result in death, be life-threatening, or require hospitalization, may be considered a serious adverse event when, based upon appropriate medical judgment, it jeopardizes the participant and may require medical or surgical intervention to prevent one of the outcomes listed in this definition.

A life-threatening adverse event is defined as any adverse experience that places the participant, in the view of the Investigator, at immediate risk of death from the event as it occurred, i.e. it does not include an event that, had it occurred in a more severe form, might have caused death. ALL serious adverse events must be reported to the Sponsor within 24 hours of the knowledge of the event and reported to the respective IRB as soon as possible but no later than ten working days after the investigator learns of the event or as required by the IRB. In the event of subject death, a copy of death records, medical records pertaining to the events leading up to the death and an autopsy report (if performed) must be sent to the Sponsor as soon as possible. All subject identifiers other than the subject number and initials must be removed from the documents submitted to the Sponsor.

A pre-existing condition is one that is present prior to or at the start of the study and is to be reported as part of the participant's medical history. It should be reported as an adverse event only if the frequency, intensity, or the character of the condition worsens during study participation.

An unexpected adverse event is one not identified in nature, severity, or frequency in the current protocol.

Adverse events (AE) data collection must begin once the Participant has signed the informed consent document. AEs will continue to be collected each visit during the entire 12 week training period and end at the 6 month visit. In general, AEs should be reported and classified by the investigator using a diagnosis. The diagnosis should be confirmed through specific signs, symptoms, and (if necessary) laboratory tests. Data to be collected will include the description of the event, onset and resolution dates (or whether the event is ongoing), severity, management/treatment, outcome, and determination of the relationship to the device used during training. The relationship of the event to the device used will be further described as related or unrelated to a specific device. If related to a device, the categories will be further described as definitely, probably, or possibly-related using the following definitions:

1. *Definitely device-related:* Any event that is associated with the device by timing and physiology, and was caused or contributed to by the device.
2. *Probably device-related:* Any event that is associated with the device by timing and physiology, and there is a good chance that it may have been caused or contributed to by the device.
3. *Possibly device-related:* Any event that is associated with the device by timing and physiology, and there is a possibility that it may have been caused or contributed to by the device.

Severity of the AE will be coded as to the degree of severity as follows:

- A. *Mild:* Awareness of the event but easily tolerated.

- B. *Moderate*: Discomfort enough to cause interference with usual activity.
- C. *Severe*: Inability to carry out usual activity (not necessarily the same as a Serious Adverse Event. Subjects may have a severe flu but not require hospitalization.)

Treatment for the AE includes all of the commercially approved products or standard procedures that are to be administered according to standard medical practice. Investigational products or procedures are not to be used as a treatment for an adverse event. All unresolved AEs should be followed by the Investigator until all events are resolved, the event is identified as being a chronic condition, or the participant is lost to follow-up.

The case report form package for this study includes dedicated adverse event and serious adverse event forms.

An independent Data Safety Monitoring Board (DSMB) will assess and adjudicate all SAEs and protocol violations.

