### **4. Study Endpoints**

The primary and secondary endpoints are as follows:

The primary endpoint is the mean increase in gait speed demonstrated during the 10MWT after 12 weeks/ 36 sessions of training and compared between groups. Both self-selected and fast speeds will be performed on the 10MWT, with the fast speed taking precedent.

The secondary endpoints of Participant outcomes related to physical performance, physiology, quality of life, and safety are to be measured at week 6/following 18 sessions (midpoint), week 12/following 36 sessions (primary endpoint), and week 24/3 months after the last session (follow-up) (unless otherwise indicated) and compared between groups.

By category, these are the following:

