**SECONDARY COMPLICATIONS**

International SCI Pain Basic Data Set

Numeric Pain Rating Scale for self-reported neuropathic pain upon resting and during gait training  
SCATS, Modified Ashworth Scale, patient-report SCI-SET, and Numeric Rating Scale for spasticity

Modified International SCI Bowel Function Basic Data Set

Modified International SCI Lower Urinary Tract Basic Data Set

Incidence of urinary tract infections per Participant

Incidence of pressure ulcers per Participant

Incidence of falls per Participant

Incidence of re-hospitalization/unexpected doctor visits per Participant

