## **10. Training Regimen and Rules**

1. The participants in Groups 1 and 2 will gait train three times per week for 45 minutes per session, ideally over twelve weeks, for a total of 36 sessions.
2. The first patient training session occurs on a separate day from the screening and baseline data collection visit(s).
3. After the 18th and 36th sessions, the evaluations (mid-point and endpoint) are to be performed on a day without a gait training session.
4. It is recommended to schedule ~75 minutes per session not only to allow for set up, adjustments, and donning and doffing time, but also potential participant tardiness and restroom breaks, as well as data collection/testing time, as needed.
5. Donning time excludes all adjustments that can be accomplished prior to patient arrival (such as hardware adjustments and software programing).
6. All 36 sessions must be completed within 15 weeks of beginning training.
7. There should be no more than 4 visits (sessions/evaluation) per week, and no more than 1 session per day.
8. No more than a two week gap in training should occur at any time.
9. Given rules 6, 7, and 8: It is recommended to plan ahead for holidays and participant vacations during the training protocol.
10. Given rules 6, 7, and 8: Evaluations may be able to occur in keeping with a regular schedule (e.g. always MWF, if the participant works) or may be scheduled as a 4th visit for the week. Keep in mind the participant's potential fatigue effects, particularly during evaluation visits, if scheduling 4 visits in a week.
11. Every effort should be made to complete sessions and assessments within the appropriate windows.
12. Total session time is to be 45 minutes, +/- 10 minutes.
13. The 5-minute warm up and 2-minute cool down are counted as part of the walking time.

Table 1A consists of the progression strategy and guidelines for Group 1 (Ekso active group) and Run-in Participants and Table 1B consists of the progression strategy and guidelines for Group 2 (Active control group).

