If the participant continues to meet criteria for this study the following data will be collected as *baseline data*. **NOTE: All Participant evaluations are conducted outside of Ekso, BWSTT, or BWS for overground walking. Baseline examinations may not occur more than 30 days prior to initiation of the training regimen:**

1. 10 Meter Walk Test (10MWT), at both self-selected and fast speeds
2. GAITRite Pressure Map for Temporospatial Gait Parameters (if site has one)
3. Timed Up and Go (TUG)
4. 6 Minute Walk Test (6MWT)
5. Spinal Cord Injury Functional Ambulation Inventory (SCI-FAI)
6. Walking Index for Spinal Cord Injury (WISCI II)
7. Upper and Lower Extremity Muscle Strength
8. Berg Balance Scale
9. The Spinal Cord Assessment Tool for Spastic Reflexes (SCATS)
10. Spinal Cord Independence Measure III (SCIM-III), Mobility subscale only, by interview
11. Modified Ashworth Scale
12. Spinal Cord Injury Spasticity Evaluation Tool (SCI-SET)

13. Numeric Rating Scale for spasticity
14. International SCI Quality of Life Basic Data Set
15. Epidemiological Studies Depression Scale (CES-D 10)
16. Borg Scale for maximal Rate of Perceived Exertion (collected at baseline 6MWT and at training session 1)
17. International SCI Pain Basic Data Set
18. Modified International SCI Bowel Function Basic Data Set
19. Modified International SCI Lower Urinary Tract Basic Data Set

See Appendix A for description of assessments.

The following data will be collected *per session*:

1. Any adverse events/complications (related to Participant or staff) noted following prior training session and during present session
2. Assessment of skin integrity of the anterior and posterior torso, anterior tibia, sacral area and bilateral feet (before and after training)
3. Walk time\*
4. Stand time\*
5. Seated rest time
6. Number of steps total and in each mode\* or number of steps at each BWS%
7. Time spent in each mode\* or time spent at each BWS%
8. Any equipment used for training, including type of assistive device and braces
9. Number of therapists/staff required at each training session to ensure the safety of the Participant and to complete the training session goals
10. Amount of assistance (e.g. min, mod, max) as reported by staff members at each training position (hips, trunk, right LE, left LE, etc.)

\* For Group 1 Participants, these data are *automatically collected* by Ekso (in Ekso Pulse) at the end of each training session

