**Footnotes (Table 2):**

† Height may be obtained verbally; weight must be measured via scale. Calculate BMI using NIH National Heart Lung and Blood Institute calculator at: [http://www.nhlbi.nih.gov/health/educational/lose\\_wt/BMI/bmicalc.htm](http://www.nhlbi.nih.gov/health/educational/lose_wt/BMI/bmicalc.htm)

\* Skin assessment to be performed before and after training sessions

• Maximum Borg to be done during session 1 then during weekly sessions (every third session) thereafter, and after 6 minute walk test during evaluations

\*\* Assessments to be performed outside of exoskeleton or any body weight support and on a non-training day.

◦ Vital signs (BP and HR) will be measured as follows:

- °° Upon relaxation (5 minutes) in sitting position after arrival. After 1 minute of standing (may hold on to something for balance or use standing in frame as needed)
- °°° Vitals should be taken in sitting before and immediately after 6 minute walk
- ↳ To be taken prior to 10MWT
- " To be taken prior to each session and needed only if orthostatic hypotension was present at the time of the previous session and/or if symptomatic upon standing at the time of the current session.

♦ Run In will follow Group 1 assessments but will not complete the follow up evaluation visit and assessments

^ To be obtained during Screening, and if participant passes screening can be used for Baseline

† Numeric Pain Scale: to be completed before and during session 1 and weekly thereafter

¤ To be done by blinded evaluator for comparison to week 6, 12, 24 (midpoint, endpoint, and follow-up) evaluation visit results.

☆ Done by blinded evaluator for comparison. Testing to be done according to ISNCSCI instructions (supine, using the correct limb positioning and angles for resistance)

 May occur over one or two visits

 B = before session, D = during session, A = after session

 Passive Group 3 will complete all evaluations at Baseline, Week 6 and week 12, the same as Groups 1 and 2, then have the option (per participant decision) to undergo 12 weeks of training using the exoskeleton or standard gait training. The optional 12 week period will consist of training only. No further evaluations will be completed at this time.

Update Concomitant Medication Log accordingly

To include shoulder flexion/extension, abduction/, and triceps

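### Four incidence endpoints (falls, urinary tract infections, pressure ulcers, unplanned care) are ascertained far more often in the trained arms than in the passive arm, with no common window, so comparisons with the passive arm are biased.

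*Protocol*

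**What the plan says.** **Endpoints.** Protocol section 4 (Secondary Complications) lists four incidence endpoints, for example "Incidence of falls per Participant"; the others are urinary tract infections, pressure ulcers, and re-hospitalisation or unexpected doctor visits. The same section has secondary endpoints measured at weeks 6, 12 and 24, "unless otherwise indicated) and compared between groups". Neither document defines a person-time rate or a cut-off for these endpoints.

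**Trained arms.** Section 10: "The participants in Groups 1 and 2 will gait train three times per week for 45 minutes per session, ideally over twelve weeks", 36 sessions in all. It also says "All 36 sessions must be completed within 15 weeks of beginning training". Among the per-session data, section 11 lists "Any adverse events/complications (related to Participant or staff) noted following prior training session and during present session", and a skin check described as "Assessment of skin integrity of the anterior and posterior torso, anterior tibia, sacral area and bilateral feet (before and after training"). Evaluations follow sessions 18 and 36, and Table 2 gives Groups 1 and 2 a week-24 visit.

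**Passive arm.** Section 8.2 schedules evaluations at weeks 6 and 12. Table 2 excludes Group 3 from week 24. Footnote 3 says of the crossover option: "The optional 12 week period will consist of training only. No further evaluations will be completed at this time". The skin-assessment row of Table 2 has no tick at the evaluation visits, although the screening list in section 11 calls for a skin check at every visit.

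**End of adverse-event collection.** Section 12 defines adverse events up to the participant's last study visit and then states: "AEs will continue to be collected each visit during the entire 12 week training period and end at the 6 month visit". That sentence is not specific to any arm.

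**The concern.** An incidence per participant depends on how often events are asked about and for how long. Here both may differ between the trained arms and the passive arm for reasons that have nothing to do with training. A participant seen three times a week is asked about a fall or a skin lesion within days. A Group 3 participant must recall it over about six weeks and, on Table 2's schedule, has no post-baseline skin check. If the trained arms' week-24 data are also set against Group 3's week-12 data, observation time is unequal too.

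At stake is whether the trial can say anything reliable about complications of gait training relative to no training. The expected direction is an apparent excess in the trained arms, against the sponsor's own device. Recorded onset dates allow a later cut at 12 weeks, but no analysis can recover events that were never elicited, so the elicitation has to be settled prospectively.

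**Working it through.** The documents give no event rate, person-time or power for these endpoints, so the plan has no figure on this point to reproduce. The arm sizes used below can be checked against Protocol section 17.4. For superiority with SDs 0.18 and 0.108, difference 0.11, 2:1 allocation, two-sided 0.05 and 80% power, the passive arm needs (0.18²/2 + 0.108²) × (1.960 + 0.842)² / 0.11² = 18.1. That rounds up to 19, with 38 for Ekso, as stated.

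**Scheduled contacts after baseline**
- Groups 1 and 2: 36 sessions + 2 evaluations = 38 by the end of training; 39 with week 24.
- Group 3 under Table 2: 2.
- Ratio: 38/2 = 19.

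Baseline is a further contact in all arms, because collection starts at consent.

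**Observation time if everything collected is used**
- Nominal: 24 against 12 weeks, ratio 2.0.
- Upper end: 15 weeks of training + 13 weeks (3 months) + 3 weeks of visit window = 31 weeks, and 31/12 = 2.6.

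**Effect with equal true rates**

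Let λ be the true rate per person-year, w the weeks observed and c the fraction of events captured.
- Expected count = λ × c × w/52.
- P(at least one recorded event) = 1 − exp(−λ × c × w/52).

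With full capture in both arms, the expected count ratio is 24/12 = 2.0 whatever λ is. If the passive arm captures 75% or 50% of events, it is 2.0/0.75 = 2.67 or 2.0/0.50 = 4.0.

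The table gives the chance that a two-sided Fisher test at 0.05, with 38 against 19 participants, declares a difference when the true rates are equal. The test is my choice, and λ and c are assumptions with no source in the documents. Percentages are false-rejection probabilities; the two P(≥1) columns assume full capture.

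| λ | P(≥1), 24 wk | P(≥1), 12 wk | 24 v 12 wk, full capture | 24 v 12 wk, passive c = 0.5 | 12 v 12 wk, full capture | 12 v 12 wk, passive c = 0.5 |
|---|---|---|---|---|---|---|
| 0.25 | 0.109 | 0.056 | 2.0% | 2.9% | 1.6% | 0.3% |
| 0.5 | 0.206 | 0.109 | 10.0% | 23.5% | 2.8% | 2.0% |
| 1 | 0.370 | 0.206 | 18.9% | 51.1% | 3.6% | 10.0% |
| 2 | 0.603 | 0.370 | 32.5% | 80.1% | 3.8% | 18.9% |

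A common 12-week window with equal capture brings the count ratio to 1.0 and false rejection below 5%. With the same window but 75% or 50% capture in the passive arm, the count ratio is still 1/0.75 = 1.33 or 1/0.50 = 2.0. The window removes the bias from duration but not the bias from asking.

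**Group 3's follow-up: passages side by side**
- Six months, no arm excepted: the Study Outline (assessment periods) has randomised participants return three months after the last session; section 12 runs adverse-event collection to the 6-month visit; section 13 speaks of retaining participants for six months.
- Week 12: Table 2 and its footnote 3.
- Crossover: section 17.1 analyses by randomised assignment whatever treatment is received, but no passage says whether events during optional training are collected for analysis, or under which arm.

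**The case against.** Several counter-arguments have force.

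- **The formal safety analysis is untouched.** SAP section 1.3 tests device-related adverse events for Ekso against active control only, and the complication-free part of the responder definition in SAP section 1.4 names the same two arms. Their sessions and follow-up are matched. This stands, and it limits the point to four secondary endpoints against a planned passive arm of 19.
- **There are common time points.** All groups are evaluated at weeks 6 and 12, onset dates are recorded, and SAP section 1.1 plans time-course displays of all complications. A 12-week cut therefore needs no new data, and no passage tells the analyst to set 24-week counts against 12-week counts. This also stands: the doubling is conditional. But neither document prescribes the cut, and dates do not repair unequal elicitation.
- **Capture need not be poor.** Hospitalisations meet the serious-event definition and must be reported within 24 hours of the site learning of them. Loss to recall may differ across falls, infections, ulcers and hospital stays. This is fair, and it is why the capture fractions are shown only as an assumed range.

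A reader might also infer that crossover events will be charged to the passive arm, so that the bias runs in both directions. The documents do not support that. If Group 3's last study visit is week 12, section 12's definition ends collection there and crossover events are not counted. If they are counted, Group 3 is observed beyond week 12 while attending sessions, and the 24-against-12 contrast no longer holds. The two readings exclude each other, and the text settles neither.

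**Conclusion.** The concern holds in limited form. For the four incidence endpoints, ascertainment is unequal between each trained arm and the passive arm: 38 scheduled post-baseline contacts against 2 by the end of training, skin checks at every session against none ticked, and a week-24 visit against none. With equal true rates, the trained arms would tend to record more events. If all collected data are used, the difference in observation time alone doubles expected counts; under the assumed rates above, it gives false-rejection probabilities from 2% to about 33%. Under-capture in the passive arm would add to this by an amount the documents do not allow one to estimate.

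It would be wrong to conclude that the trial's safety comparison as a whole is invalid. Ekso against active control is unaffected, and the primary endpoint is not involved. The conflict over Group 3's follow-up, and the silence on crossover events, are separate matters that the passages leave open. This should be corrected, but it does not threaten the main result.

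**What to change.** 1. Limit three-arm comparisons of these endpoints to a common window from baseline. Either cut by onset date at a fixed calendar time such as 12 weeks, or use events per person-time up to the endpoint evaluation. The window should not be defined by session 36 alone, because training may run to 15 weeks.
2. Ask the same structured recall questions and do the same skin check at the existing week 6 and week 12 evaluations in all arms, and base the three-arm comparison on these. This reduces the difference but may not remove it: participants questioned at 36 sessions may recall better.
3. Use session-reported and week-24 events only for Ekso against active control.
4. Tabulate any crossover-period events separately by device used, and exclude them from the passive-arm count.
5. Reconcile the Study Outline, sections 12 and 13, and Table 2 with its footnote 3 on when Group 3's follow-up and adverse-event collection end. Reconcile the skin-assessment row of Table 2 with section 11.

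The cost is a short questionnaire and a skin check at two existing visits, a few lines in the protocol and SAP, and fewer events in the three-arm comparison.

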### **13. Participant Termination**

Participants will be advised that they may voluntarily withdraw from the study at any time and will be instructed to notify the investigator immediately if they choose to withdraw. Participants may choose to withdraw for any reason and are not obligated to reveal their reason(s) for withdrawal. Should Participants withdraw prior to follow-up completion, they will be asked to complete the final questionnaires if withdrawn prior to the end of the participation period. In addition, Participants may be involuntarily withdrawn by the investigator if the investigator believes it is in the best interests of the Participant (e.g., adverse event that prevents further visits).

If a Participant is lost to follow up, the End of Study CRF must be completed and submitted to the data manager as soon as possible. If a Participant fails to comply with the follow up evaluations, the study site must attempt to contact the Participant at least three times, including once as a registered letter.

In order to minimize loss to follow-up, at the baseline evaluation visit the study coordinator will request that the Participant provide names and contact information of two individuals who have a close relationship with the Participant. The contacts will be utilized in the event that the Participant relocates or cannot be reached by mail or telephone. This information will be treated as confidential and for use by the investigative site only. Every effort will be made to retain Participants for the entire 6 months of follow up.

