The following data will be collected *at every 3rd session* (i.e. session 3, 6, 9, etc.,(refer to Table 2):

1. 10MWT without braces at self-selected speed
2. Borg Scale for maximal RPE during intervention and overground training
3. Numeric Pain Rating Scale of neuropathic pain during rest and during the intervention
4. Numeric Rating Scale for spasticity
5. NASA – Participant Task Load Index
6. Heart rate and blood pressure

Therapist assessments include the following:

1. NASA-Task Load Index
2. Video Assessment of therapist posture during sessions 1 and 36
3. Borg Scale for maximal RPE during intervention and overground training
4. Reports of injuries or pain (includes all treating staff)

Table 2 shows the list of Participant assessments and data collection intervals. Therapist measures are included in Table 3.

Table 2 - Participant Assessments and Data Collection Intervals	Screening Visit	Baseline Visit	Session Assessments GROUPS 1 & 2 (and Run In) Sessions 1-36			Evaluations ALL GROUPS (including Run In) After session 18 Week 6** Midpoint (+/- 1 week of completing session 18)	Evaluations ALL GROUPS (including Run In) After session 36 Week 12** Endpoint (+/- 1 week of completing session 36)	Evaluations GROUPS 1 & 2 only (Not Run-In or Group 3 Participants) Week 24** Follow-Up, 3 months following the last training session (+/- 3 weeks)
	Assessment		Week 0 (Not > 30 days prior to first training session)	B	D	A		
Physician Clearance		✓						
Demographics ^	✓							
Medical History ^	✓							
Concomitant Medications 	✓	✓	✓			✓	✓	✓
BMI ^‡	✓	✓				✓	✓	✓
Vital Signs °^	✓°°	✓°°°	✓°°			✓°°°	✓°°°	✓°°°
ROM: Hip, Knee, Ankle ^	✓							
UE MMT  ^	✓							
Skin Assessment 	✓	✓	✓	✓				
Modified Ashworth Scale	✓	✓¤				✓	✓	✓
SCATS		✓				✓	✓	✓
UEMS	✓	✓☆				✓☆		✓☆
LEMS	✓	✓☆				✓☆		✓☆
Full ISNCSCI Exam ^	✓						✓	

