## **17. Statistical Methods**

### **17.1 General Principles**

The primary analysis for all baseline characteristics and study outcomes will include all available data for all enrolled subjects. Standard summary statistics will be calculated for all study variables. For continuous variables, statistics will include means, standard deviations, medians and ranges. Categorical variables will be summarized in frequency distributions.

Statistical analyses will be conducted according to the principles of intent-to-treat, under which subjects will be evaluated according to their randomized assignment regardless of the treatment actually received. P-values for tests of superiority will be two-sided and for non-inferiority one-sided, with values less than 0.05 deemed statistically significant.

Statistical analyses will be conducted in SAS version 9.3 or above (SAS Institute, Cary, N.C.), R version 3.2 or above (R Foundation for Statistical Computing, Vienna, Austria, <http://www.R-project.org>) or another validated statistical software package.

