**Table 4 – Planned Participant Assessments and Assessment Windows**

Time point	Window
Baseline	No more than 30 days prior to start of training
6 Weeks(after 18 session)	No more than 1 week after session 18
12 Weeks (after 36 session)	No more than 1 week after session 36
6 Months	+/- 3 weeks

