### **1.7 Lost to Follow-up**

Data on subjects who are lost to follow-up or who withdraw from the study will be maintained and analyzed up to the point at which they discontinued. The reason for withdrawal will be recorded if known. Subjects who discontinue participation, for whatever reason, will remain in the study and be subject to follow-up in the same manner as those who complete the study except as noted above. The only confirmed lost to follow-up subject will be the subject who dies or refuses to continue to participate in the study and thereby withdraws.

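### No calendar-dated 12-week 10MWT is scheduled for a trained participant who does not complete 36 sessions, and Protocol Section 13 and SAP 1.7 do not agree on what follows

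*Protocol*

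**What the plan says.** - **Withdrawal.** Protocol Section 13 covers participants who leave the study, by choice or by the investigator's decision. For those who leave before follow-up is complete, "they will be asked to complete the final questionnaires if withdrawn prior to the end of the participation period". No walking test is named.
- **Endpoint visit, Groups 1 and 2.** Table 4 gives the window as "No more than 1 week after session 36". Table 2 sets it at one week either side of completing session 36, and Section 10 rule 3 places it after the 36th session. Week 12 appears only as a label.
- **Training limits.** Section 10 rule 6 reads "All 36 sessions must be completed within 15 weeks of beginning training", and rule 8 limits gaps to two weeks. Neither says when to evaluate a participant who falls outside the limit.
- **Endpoint visit, Group 3.** Table 2 footnote 3 places these evaluations at weeks 6 and 12.
- **SAP 1.7.** Those who discontinue, for any reason, "will remain in the study and be subject to follow-up in the same manner as those who complete the study except as noted above". Earlier in the same paragraph, data on subjects lost or withdrawn "will be maintained and analyzed up to the point at which they discontinued". Only death or refusal counts as confirmed loss to follow-up.
- **Analysis.** Under Section 17.1, "subjects will be evaluated according to their randomized assignment regardless of the treatment actually received". Section 18.1 does not impute missing values and allows last observation carried forward as exploratory only.

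**The concern.** An intent-to-treat comparison needs the 12-week walking speed of participants who stopped training as well as of those who finished. In the two trained arms, the event that dates the endpoint visit is completion of the treatment. A Group 1 participant who stops at session 20 but is willing to attend has no endpoint date; a Group 3 participant does. If sites follow the protocol's tables, the primary outcome will tend to be missing for participants who stopped because of poor tolerance or lack of progress, and both primary comparisons will lean towards those who finished. A 12-week value that was never measured cannot be recovered at analysis.

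**Working it through.** **1. Which 10MWT values exist for an early stopper in Group 1 or 2**

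| Measurement | Speed | Why it does not replace the endpoint value |
|---|---|---|
| Every third session (Section 11) | Self-selected, no braces | Section 4 gives fast speed precedence, and the series ends when training stops |
| Midpoint, after session 18 | Both | Taken about week 6, before the endpoint |
| Endpoint, dated from session 36 | Both | Has no date if session 36 is not reached |
| Follow-up, three months after the last session | Both | Can be dated, but is a different time point |

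The follow-up visit is itself dated in two ways. For someone who stops at week 4, three months after the last session is about week 4 + 13 = 17. Table 4 says six months, which is about week 26 if counted from the start of training; Table 2 labels the visit week 24. The two datings lie 7 to 9 weeks apart.

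**2. The plan's own figures reproduce**

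Inputs from Section 17.4: change (SD) of 0.11 (0.18) m/s for Ekso, 0.078 (0.108) for active control and 0 (0.108) for passive control. Section 17.2 gives the margin, 0.055 m/s.

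- Superiority, 38 against 19, unequal-variance t test, two-sided 0.05: SE = √(0.18²/38 + 0.108²/19) = 0.0383; 0.11/0.0383 = 2.87; power 80.5%.
- Non-inferiority, 37 per group, one-sided 0.05: SE = √((0.18² + 0.108²)/37) = 0.0345; (0.032 + 0.055)/0.0345 = 2.52; power 80.3%.
- Total: 38 + 38 + 19 = 95. The gap to 127 is (127 − 95)/127 = 25.2%.

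With 127 randomised (about 51/51/25) and 25% of each trained arm missing, 38/38/25 remain. Power is then about 85% for superiority and 81% for non-inferiority. The issue is therefore bias, not power.

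**3. Size of the bias under stated assumptions**

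Assume completers gain the planned amount, stoppers gain g, and stoppers' 12-week values are missing. The stopping proportions s are assumptions, because the documents give none.

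Overstatement of the Ekso mean = s × (0.11 − g):

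| s | g = 0 | g = 0.055 (half) |
|---|---|---|
| 10% | 0.011 | 0.0055 |
| 20% | 0.022 | 0.011 |
| 25% | 0.0275 | 0.014 |

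At 25% and zero gain this is 0.0275/0.055 = half the margin. If the passive mean is zero as planned, the same amount carries into Ekso minus passive control.

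For Ekso minus active control with zero gain among stoppers, bias = s(Ekso) × 0.11 − s(active) × 0.078:

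| Ekso stop | Active stop | Bias (m/s) |
|---|---|---|
| 25% | 10% | 0.0275 − 0.0078 = +0.020 |
| 25% | 25% | 0.0275 − 0.0195 = +0.008 |
| 10% | 25% | 0.0110 − 0.0195 = −0.009 |

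A positive value favours Ekso. If stoppers gain half their own arm's planned change, the first row becomes 0.25 × 0.055 − 0.10 × 0.039 = +0.010.

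**The case against.** A reader might infer that the 10MWT is never measured once a participant stops training. The documents do not support that. SAP 1.7 keeps discontinuers in follow-up, the follow-up 10MWT can be dated from the last session, Section 13 promises every effort at retention and requires three contact attempts, and Section 18 says missed visits should be made up. Nor does Section 13 say that stopping training is withdrawal; it is silent on that case. Its adverse-event example is one that prevents further visits, and such a participant could not walk the test under any wording. Nothing states that breaching the gap rule or the 15-week limit cancels the evaluation.

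The contrast between arms also has limits. Section 13 applies to Group 3 as well, and Groups 1 and 2 share the same visit rules, so non-inferiority is not biased towards Ekso by construction. Section 17.4 attributes the gap between 95 and 127 to attrition and to variance from the postulated effects together, so 25% is not a planned dropout rate. The intent-to-treat population remains all randomised subjects; missing endpoints weaken that analysis without turning it into a completers' analysis by definition.

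All of this stands. It does not supply a date for the 12-week test. SAP 1.7 qualifies its follow-up sentence by what precedes it, and what precedes it ends the data at discontinuation for those who withdraw. A general promise to retain participants, or to make up visits within their window, gives no date when the window is defined by a session that never takes place.

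**Conclusion.** The concern holds in this form: as written, no 12-week 10MWT is scheduled for a Group 1 or 2 participant who does not complete 36 sessions; Section 13 asks those who withdraw only for questionnaires and does not address stopping training alone; and SAP 1.7 is at odds with Section 13 and unclear within itself about data after discontinuation. For 10% to 25% early stopping, the Ekso mean would be overstated by 0.011 to 0.0275 m/s with zero gain among stoppers, or by 0.0055 to 0.014 m/s with half the planned gain. The bias against active control runs from about +0.020 to −0.009 m/s over the zero-gain cases shown, so its direction is not known in advance. These sizes rest on assumed stopping rates and gains; the gap in scheduling rests on the text alone.

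**What to change.** - **Section 13.** Distinguish stopping training from withdrawing from the study. Ask every randomised participant who stops training, or who withdraws but is willing and able to attend, to complete the existing blinded evaluation, including the 10MWT at both speeds.
- **Tables 2 and 4.** Add a calendar-based date for the endpoint evaluation of Group 1 and 2 participants who do not complete session 36, set so that it also works for those still training up to the 15-week limit. Reconcile the two datings of the follow-up visit.
- **SAP 1.7.** Limit the sentence that ends data at discontinuation to those who withdraw consent or are lost. State that 10MWT values collected after stopping training enter the intent-to-treat analysis. Make the handling of participants who cannot be contacted consistent with Section 13; that section has contact steps but no definition of loss to follow-up to borrow, so one must be written.

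The cost is protocol and SAP wording, using visits and evaluators already planned. The downside is a few extra visits for participants no longer training and a possibly smaller observed effect. The sample size does not change.
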